12.5. COLUMBIA SUICIDE SEVERITY RATING SCALE

The Columbia Suicide Severity Rating Scale (C-SSRS) will be listed for both protocol parts separately using the SAS.

The information for these presentations will be obtained from the following eCRFs:

- C-SSRS Screening
- C-SSRS Since Last Visit

The C-SSRS responses over time will be tabulated using count and percent by treatment groups throughout the study, using SAS.

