	Screening D -28 to D -2a	D-2ª	D-1 ^a	DIa	D2-6ª	D8	D9-13a	D15ª	D16-20ª	D22ª	D23-27a	D29a	D30-34ª	D36 a	D64a	D104ª	E/D ^b	
				100			Gene	ral an	d Sa	fety A	Asses	smen	ts					
Informed consent	X																	
Eligibility criteria	X		X															Recheck eligibility before randomization and/or first dose of study drug
Medical history ^c (includes substance usage)	X	X	x															Medical occurrences that begin before the start of study drug but after obtaining informed consent will be recorded on the Medical History/Current Medical Conditions section of the CRF, not the AE section
Demography	X			e.v		1,0			98									
Physical and neurological examination	X		X											X		X	X	Physical examination will include height (screening only) and weight measurements; see also Section 8.2.1
Randomization			X															
Vital signs	х		X	X		x		x		X		x		X	X	X	X	Pre-dose, then 2 and 6 hours after the end of the study drug infusion on D1, D8, D15, D22, D29; otherwise once on the days indicated; see Section 8.2.2 for vital signs assessments

CONFIDENTIAL Page 26 of 101

Protocol TB006AD2102

Protocol Date and Version: 15 Oct 2021; v 3.0

Table 2. Part	2 - Sche	dule	of A	ctivit	ies													
	g -2ª						St	udy I	Drug	Adm	inisti	ation	ı Per	iod				Notes
	Screening D -28 to D -2	D -2ª	D-1ª	D1ª	D2-6ª	D8	D9-13ª	D15a	D16-20ª	D22ª	D23-27a	D29a	D30-34a	D36 a	D64ª	D104ª	E/D ^b	
12-lead ECG	X		X	X		X		X		х		Х		х		X	X	D1, D8, D15, D22, D29: pre-dose, then after end of study drug infusion D-1, D36, D104, E/D: time-matched with D1, D8, D15, D22, D29 pre-dose to the extent possible
AE monitoring				X	X	X	X	X	X	X	X	X	X	X	X	x	x	All AEs and SAEs will be collected from the time of the first study drug administration until D104.
Prior/concomitant medication review	X	X	X	X	X	X	X	X	X	X	X	X	X	X	X	X	X	
C-SSRS	X			X		X		X		X		X		X	X	X	X	
Clinical unit confinement		х	X	х		x		x		х		X						At least 6 hours following study drug administration on dosing days; discharge from the clinical unit will be at the discretion of the investigator provided there are no safety concerns identified from review of the clinical data. Optional overnight confinement from either D -2 or D -1 and on days prior to other dosing days (D7, D14, D21, D28)

CONFIDENTIAL Page 27 of 101

Protocol TB006AD2102

Protocol Date and Version: 15 Oct 2021; v 3.0

Table 2. Part 2	- Sche	dule	of A	ctivit	ies													
	-2ª						St	udy I	Drug	Adm	inisti	ation	n Per	iod				Notes

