8.2.5 Suicidal Ideation and Behavior Risk Monitoring

The C-SSRS is a prospective semi-structured interview comprised of the following areas of assessment: Ideation, Intensity of Ideation, Behavior, and Lethality. It has been used extensively in global clinical studies (academic and industry sponsored) and in a range of therapeutic areas, disorders and indications, including psychiatry, neurology, obesity, urology and endocrinology and is FDA-approved. It has been used to determine eligibility to enroll at screening and at every follow-up visit to prospectively monitor suicidality during the study. The C-SSRS was developed for use in clinical studies and can be administered by non-mental health professionals with training. All C-SSRS raters for this study will have a certificate that verifies training completion and allows them to rate in this study.

Protocol TB006AD2102

Protocol Date and Version: 15 Oct 2021; v 3.0

There are 2 versions of the C-SSRS. The "Past 6 months" version of the C-SSRS will be completed at screening and the "Since Last Visit" version will be completed at all remaining visits according to the SoA (Table 1 and Table 2). The "Since Last Visit" version will also be completed at any unscheduled clinic visits.

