9.4.2 Part 1 Primary Endpoints

9.4.2.1 Safety and Tolerability

All AEs will be coded using the most recent version of MedDRA. The incidence of AEs will be summarized by SOC and PT. Similar summaries will be produced for AEs by severity, SAEs, treatment related AEs, and AEs leading to discontinuation. AEs are collected from the first dose of study drug, thus all AEs are considered treatment emergent AEs.

The ECG results will be presented by visit, summarizing the continuous measurements based on the average of triplicate values, including the QT, QTc, QRS, RR, PR intervals, as well as change from baseline values, and clinically significant changes in heart rate and rhythm.

Reported values and change from baseline values of hematology, clinical chemistry and urinalysis (and the determinations relevant to the normal ranges and appropriate clinically significant or CTCAE toxicity gradings) will be summarized by laboratory test for each assessment day, using appropriate descriptive statistics.

Vital signs (systolic and diastolic blood pressure, pulse rate, respiratory rate, and oral temperature) will be summarized by assessment day showing absolute values, change from baseline values, and clinically significant changes (including orthostasis) using appropriate descriptive statistics.

Physical and neurological examinations will be summarized by assessment day showing shift from baseline.

Protocol TB006AD2102

Protocol Date and Version: 15 Oct 2021; v 3.0

The C-SSRS assessments will be presented in a by-subject listing.

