9.7. VISIT WINDOWS/UNSCHEDULED VISITS

No mapping/renaming of visits (unscheduled or otherwise) will be done for this study. That is, only regular scheduled visit data will be used for summarization in tables. However, all collected data will be listed.

Unscheduled visits will be considered eligible for Baseline values. Unscheduled visit results will also be considered eligible for testing of potentially clinically significant (PCS) values (laboratory, Electrocardiogram (ECG) and vital signs).

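### The SAP specifies no per-patient post-dose C-SSRS summary by arm, and its rule on unscheduled visits can leave a suicidality event out of every C-SSRS table

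*SAP*

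**What the plan says.** SAP 12.5 plans two outputs. The first is a listing: "The Columbia Suicide Severity Rating Scale (C-SSRS) will be listed for both protocol parts separately using the SAS". The second is a table: "The C-SSRS responses over time will be tabulated using count and percent by treatment groups throughout the study, using SAS" (SAS here is the safety analysis set). Protocol 9.4.2.1 plans less: "The C-SSRS assessments will be presented in a by-subject listing".

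Protocol 8.2.5 sets the forms. A six-month look-back version is used at screening. After that the Since Last Visit version is used: this "version will be completed at all remaining visits according to the SoA", and the same "version will also be completed at any unscheduled clinic visits". In both Parts the schedule of activities places C-SSRS at screening, Days 1, 8, 15, 22, 29, 36, 64 and 104, and early discontinuation.

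Two general SAP rules apply. Section 9.2 takes the last value before first dose as baseline. Section 9.7 states that "only regular scheduled visit data will be used for summarization in tables". It lets unscheduled results count only towards baseline and towards clinically significant laboratory, ECG and vital-sign values.

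C-SSRS is a primary safety endpoint in Part 1 and a secondary one in Part 2 (Protocol section 3; SAP 6.3).

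**The concern.** The safety question is how many patients in each arm had suicidal ideation or behaviour after dosing, and in how many it was new or worse than before. SAP 12.5 specifies no summary that answers it. Laboratory, ECG and vital-sign results each get abnormality tables, many of them referenced to baseline, but C-SSRS has no counterpart.

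A table of responses over time does not fill the gap. A patient with recurring ideation appears at several visits, while a patient with a single episode appears at one. The visit counts do not show which has happened.

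The rule on unscheduled visits adds a capture problem. A discrete event that brings a patient in between visits is recorded on a form that the tables leave out, and later forms need not ask about it again.

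**Working it through.** The documents give no figure for the C-SSRS analysis, so there is none to reproduce.

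**1. Can visit counts be turned into patients?** Inputs are the seven scheduled post-dose forms (Days 8, 15, 22, 29, 36, 64 and 104) and about 58 patients per arm in Part 2 (SAP 6.1.1). Suppose each form shows one positive in an arm.

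- If it is the same patient throughout: 1/58 = 1.7%.
- If it is seven different patients: 7/58 = 12.1%.

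The planned table is identical in both cases.

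**2. What happens to an unscheduled form?**

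- Protocol 8.2.5: a Since Last Visit form is completed at the unscheduled visit.
- SAP 9.7: that form is listed but not tabulated. The exceptions do not include post-dose C-SSRS.
- The next scheduled form, read literally, starts its recall at the unscheduled visit.

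An event that was over by then appears on no tabulated form. Ideation that continues would still be picked up at the next scheduled visit.

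**3. Recall length (secondary point).** Recall is the difference between consecutive scheduled C-SSRS days, starting from Day 1.

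| Form | Nominal recall (days) | Ratio to a weekly form | Share of 103 days |
|---|---|---|---|
| Days 8, 15, 22, 29, 36 (each) | 7 | 1.0 | 6.8% |
| Day 64 | 28 | 28/7 = 4.0 | 27.2% |
| Day 104 | 40 | 40/7 = 5.7 | 38.8% |

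The last two forms cover 68/103 = 66% of post-dose time.

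Event rates are not in the documents, so a range is assumed. With cumulative risk c over 103 days and constant hazard, λ = −ln(1 − c)/103. The chance of a new event on a form with recall g is 1 − exp(−λg).

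| Assumed c | Weekly form | Day 64 | Day 104 |
|---|---|---|---|
| 2% | 0.14% | 0.55% | 0.78% |
| 5% | 0.35% | 1.38% | 1.97% |
| 10% | 0.71% | 2.82% | 4.01% |
| 20% | 1.51% | 5.89% | 8.30% |

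The ratios to a weekly form stay at 3.9 to 4.0 (Day 64) and 5.5 to 5.7 (Day 104) across this range. If Day 64 is missed, the Day 104 form covers 68 days, or 68/7 = 9.7 times a weekly form. With ±2 days on each visit, a nominal 7-day gap can be 3 to 11 days.

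**4. What a per-patient summary would give.** One yes/no per patient yields one share per arm. At an assumed 5% cumulative risk that is 58 × 0.05 = 2.9 patients expected. If none of 58 is positive, the one-sided 95% upper bound is 1 − 0.05^(1/58) = 5.0%. The planned table supports neither statement directly.

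**The case against.** Several points on the other side carry weight.

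- **The layout is not settled.** SAP 12.5 speaks of responses over time, and SAP 9.1 leaves layout to mock shells that were not available. A reader might infer that no such table will be produced. The documents support only that the SAP does not specify one.
- **The listing holds the information.** SAP 9.7 lists all collected data, including unscheduled visits. In Part 1, with six active patients per dose and six on placebo in total, affected patients can be counted by eye. In Part 2, with about 116 patients, a listing is not a prespecified comparison between arms.
- **Adverse event tables are a second route.** Protocol 10.2.1 counts abnormal safety assessments as adverse events when the investigator judges them clinically significant, and suicidality is not among the exempted disease-related events. However, nothing requires a positive C-SSRS to be reported as an adverse event. This narrows the gap without closing it.
- **The late rise is limited.** A reader might infer that unequal recall distorts the treatment comparison. It does not: both arms follow the same schedule, so recall is nominally equal at each visit. The rise is within arm and concerns new events only. Ideation that is positive on every form shows no such pattern.
- **Day 1 is already handled.** A reader might infer that the Day 1 form is treated as on-treatment data. SAP 9.2 makes the last pre-dose value the baseline and assumes an untimed Day 1 assessment is pre-dose. What remains is that this rule sets aside the six-month screening history as a comparator.

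**Conclusion.** The concern holds as a gap in a safety summary. As written, the SAP specifies no per-patient post-dose C-SSRS result by arm. The by-visit counts cannot supply one (1.7% to 12.1% in the example), and an event recorded at an unscheduled visit can be absent from every C-SSRS table. Neither the listings nor the adverse event tables replace the missing summary in Part 2.

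No planned efficacy or safety result becomes wrong, and it does not follow that a signal would be hidden altogether, because the data are still listed. The recall effect (about 4 times at Day 64 and 5.5 to 5.7 times at Day 104) is a matter of reading the display correctly and does not bias the treatment comparison.

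The conclusion rests on a literal reading of Since Last Visit and of SAP 9.7, on nominal visit days, and on mock shells that were not seen. Event rates are assumptions. The first two findings do not depend on them, and the recall ratios hardly do.

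**What to change.** In SAP 12.5:

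1. Keep the by-visit table and footnote the recall period of each form (nominally 7, 28 or 40 days after dosing).
2. Add a table, mainly for Part 2, of the number and percent of patients in each arm with (a) any post-dose suicidal ideation, (b) any post-dose suicidal behaviour, and (c) an ideation or behaviour category that is new or worse than the worst of the pre-dose forms (screening and Day 1).
3. State that the worst-pre-dose comparator in (c) is an exception to the last-value baseline rule in SAP 9.2.
4. State that the table counts every form completed after first dose, including early-discontinuation and unscheduled forms, as an exception to SAP 9.7.

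In Part 1 the listing nearly suffices, so the table is optional there. The cost is one table per Part at most, a footnote and a few SAP sentences. No new data are collected and study conduct does not change.

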13. OTHER RELEVANT DATA ANALYSES/SUMMARIES

13.1. HOSPITALIZATIONS AND CLINICAL UNIT CONFINEMENT

A combined listing on the following items will be presented using the SAS separately for both protocol parts:

- Hospitalizations
- Clinical unit confinement

The information for these presentations will be obtained from the following eCRFs:

- Adverse Events Details eCRF
- Clinical Unit Confinement

Duration per hospital stay is calculated in days as:

$$\text{Hospitalization Duration (days)} = (\text{Discharge Date} - \text{Admission Date}) + 1$$

Duration of clinical unit confinement is calculated in days as:

$$\text{Clinical Unit Confinement Duration (days)} = (\text{Discharge Date} - \text{Admission Date}) + 1$$

It should be noted that the above duration definitions consider part of a day to count as a whole day.

13.2. PHYSICAL AND NEUROLOGICAL EXAMINATIONS

A listing of physical and neurological examination findings for both protocol parts will be presented separately using the SAS.

The information for the listing will be obtained from the following eCRFs:

- Physical and Neurological Examination
- Physical and Neurological Exam Abnormalities

It should be noted that weight will be presented and summarized alongside the vital signs (see Section 12.4 for details), and height will be presented alongside demographics and baseline characteristics (see Section 10.2 for details).

Body systems to assess include:

-
- Cardiovascular
 - Respiratory
 - Gastrointestinal
 - Neurological (Mental status, Motor and Sensory Skills, Hearing and Speech, Vision, Coordination, Balance)

13.3. IMMUNOGENICITY ANALYSIS

To assess the immunogenicity of TB006, the presence of anti TB006 antibodies, and associated titer values will be listed by patient and time point for both protocol parts using SAS.

The anti-drug antibody titer values will be summarized descriptively for all subjects, by treatment groups and baseline AD severity stratifications (for Part 2 only), using SAS. Also, the status of anti-drug antibody will be tabulated by treatment groups and baseline AD severity stratifications (for Part 2 only), using SAS.

15. APPENDICES

Appendix I: SCHEDULE OF ASSESSMENTS AND PROCEDURES

Table 5. Part 1 - Schedule of Activities

	Study Drug Administration Period														Notes	
	Screening D -28 to D -2 ^a	D -2 ^a	D -1 ^a	D1 ^a	D2-6 ^a	D8	D9-13 ^a	D15 ^a	D16-20 ^a	D22 ^a	D23-27 ^a	D29 ^a	D30-34 ^a	D36 ^a	D64 ^a	D104 ^a
General and Safety Assessments																
Informed consent	X															
Eligibility criteria	X		X													Recheck eligibility before randomization and/or first dose of study drug
Medical history ^c (includes substance usage)	X	X	X													Medical occurrences that begin before the start of study drug but after obtaining informed consent will be recorded on the Medical History/Current Medical Conditions section of the CRF, not the AE section
Demography	X															
Physical and neurological examination	X		X									X		X	X	Physical examination will include height (screening only) and weight measurements; see also Section 8.2.1 of Protocol
Randomization			X													
Vital signs	X		X	X	X	X	X	X	X	X	X	X	X	X	X	Pre-dose, then 2 and 6 hours after the end of the study drug infusion on D1, D8, D15, D22, D29; otherwise once on the days indicated; see Section 8.2.2 of Protocol for vital signs assessments

Table 5. Part 1 - Schedule of Activities

	Screening D-28 to D-2 ^a	D-2 ^a	D-1 ^a	Study Drug Administration Period													Notes
				D1 ^a	D2-6 ^a	D8	D9-13 ^a	D15 ^a	D16-20 ^a	D22 ^a	D23-27 ^a	D29 ^a	D30-34 ^a	D36 ^a	D64 ^a	D104 ^a	
12-lead ECG	X		X	X	X	X	X	X	X	X	X	X	X	X	X	X	D1, D8, D15, D22, D29: pre-dose, then 2 and 6 hours after end of study drug infusion D -1, D36, D64, D104, E/D: time-matched with D1, D8, D15, D22, D29 pre-dose to the extent possible
AE monitoring				X	X	X	X	X	X	X	X	X	X	X	X	X	All AEs and SAEs will be collected from the time of the first study drug administration until D104.
Prior/concomitant medication review	X	X	X	X	X	X	X	X	X	X	X	X	X	X	X	X	
C-SSRS	X			X		X		X		X		X		X	X	X	
Clinical unit confinement		X	X	X		X		X		X		X					At least 6 hours following study drug administration on dosing days; discharge from the clinical unit will be at the discretion of the investigator provided there are no safety concerns identified from review of the clinical data. Optional overnight confinement from either D -2 or D -1 and on days prior to other dosing days (D7, D14, D21, D28)
Outpatient visit			X										X	X	X	X	If the patient is not overnight confined on D -1 (see above), the D -1 visit will be an outpatient visit

Table 5. Part 1 - Schedule of Activities

	Screening D-28 to D-2 ^a	D-2 ^a	D-1 ^a	Study Drug Administration Period												Notes	
				D1 ^a	D2-6 ^a	D8	D9-13 ^a	D15 ^a	D16-20 ^a	D22 ^a	D23-27 ^a	D29 ^a	D30-34 ^a	D36 ^a	D64 ^a	D104 ^a	
Site to contact patient					X		X		X		X		X				Investigator or designee to telephone the patient between D2-6, D9-13, D16-20, D23-27, and D30-34
Central Laboratory Assessments																	
Viral serology (HBsAg, IGM anti-HBc, anti-HCV, HIV) and COVID-19	X																
Urine alcohol	X		X								X		X				Locally performed at site
Drug screening	X		X								X		X				
Clinical laboratory tests (clinical chemistry, hematology, urinalysis)	X		X		X			X				X		X	X		
Pharmacodynamic Assessments: Cognition Testing, MRI, Blood Samples																	
MMSE	X		X				X					X	X	X	X		
Clinical Dementia Rating scale			X				X					X	X	X	X		
Cognitive Drug Research Dementia Rating battery ^d	X		X		X		X		X		X	X	X	X	X		
NPI			X									X	X	X	X		
Blood sample for PD assessment			X									X		X	X	Fluid biomarkers will be determined in plasma	
Study Treatment																	
Study drug IV infusion				X	X	X	X	X	X	X							

Table 5. Part 1 - Schedule of Activities

	Screening D-28 to D-2 ^a	D-2 ^a	D-1 ^a	Study Drug Administration Period												Notes
	D1 ^a	D2-6 ^a	D8	D9-13 ^a	D15 ^a	D16-20 ^a	D22 ^a	D23-27 ^a	D29 ^a	D30-34 ^a	D36 ^a	D64 ^a	D104 ^a	E/D ^b		
Pharmacokinetics																
Blood sample for PK assessment				X	X					X		X	X	X	X	Pre-dose, end of infusion, then 1, 2, 4, and 6 hours after the end of infusion on D1, D8, and D29; single time point on other days
Blood sample for ApoE4 genotyping	X															Optional ApoE4 sampling is collected at screening but can be taken at any visit until the last study visit (Section 8.7 of Protocol)
Pharmacokinetics and Pharmacodynamics																
Blood sample for ADA assessment				X	X						X		X			ADA assessment is performed on blood sample collected for PK assessments; D1 and D8 assessment is performed on the pre-dose sample
Lumbar puncture for CSF collection ^e			X								X					Lumbar puncture indicated for D-1 can be performed any time between D-8 and D-1 CSF biomarkers, and TB006 levels will be determined in CSF

AD = Alzheimer's Disease; ADA = anti-drug antibody; AE = adverse event; anti-HCV = hepatitis C virus antibody; ApoE4 = apolipoprotein E4; COVID = coronavirus disease; CRF = case report form; C-SSRS = Columbia Suicide Severity Rating Scale; CSF = cerebrospinal fluid; D = Day; DSM-5 = Diagnostic and Statistical Manual of Mental Disorders, Fifth Edition; ECG = electrocardiogram; E/D = Early Discontinuation; HBsAg = hepatitis B surface antigen; IgM anti-HBc = immunoglobulin M antibody to hepatitis B core antibody; IV = intravenous(ly); MMSE = Mini-Mental State Examination; [REDACTED] NINCDS-ADRDA = National Institute of Neurological and Communicative Disorders and Stroke – Alzheimer's Disease and Related Disorders Association; NPI = Neuropsychiatric Inventory; PD = pharmacodynamic(s); [REDACTED] PK = pharmacokinetic(s); SAE = serious adverse event.

a Visit days and procedures are allowed a window of ± 2 days from Day 1 to End of Treatment.

b Applicable only for patients who discontinue early from the study.

- c The medical history assessed at the screening visit should include prior AD treatment assessment(s). Establishing the clinical diagnosis of AD should include use of criteria from the DSM-5 – Criteria for Major Neurocognitive Disorder (previously dementia) (Section 10.4 of Protocol, Appendix 4) and the NINCDS-ADRDA (Note: ADRDA is now the Alzheimer's Association) (Section 10.5 or Protocol, Appendix 5).
 - d The Cognitive Drug Research battery is to be performed twice during the screening visit in both Part 1 and Part 2.
 - e The lumbar puncture procedure is optional.
-

Table 6. Part 2 - Schedule of Activities

	Study Drug Administration Period													Notes		
	Screening D-28 to D-2 ^a	D-2 ^a	D-1 ^a	D1 ^a	D2-6 ^a	D8	D9-13 ^a	D15 ^a	D16-20 ^a	D22 ^a	D23-27 ^a	D29 ^a	D30-34 ^a	D36 ^a	D64 ^a	D104 ^a
General and Safety Assessments																
Informed consent	X															
Eligibility criteria	X		X													Recheck eligibility before randomization and/or first dose of study drug
Medical history ^c (includes substance usage)	X	X	X													Medical occurrences that begin before the start of study drug but after obtaining informed consent will be recorded on the Medical History/Current Medical Conditions section of the CRF, not the AE section
Demography	X															
Physical and neurological examination	X		X								X		X	X		Physical examination will include height (screening only) and weight measurements; see also Section 8.2.1 of Protocol.
Randomization			X													
Vital signs	X		X	X	X	X	X	X	X	X	X	X	X	X	X	Pre-dose, then 2 and 6 hours after the end of the study drug infusion on D1, D8, D15, D22, D29; otherwise once on the days indicated; see Section 8.2.2 of Protocol for vital signs assessments

Table 6. Part 2 - Schedule of Activities

	Screening D-28 to D-2 ^a	Study Drug Administration Period															Notes
		D-2 ^a	D-1 ^a	D1 ^a	D2-6 ^a	D8	D9-13 ^a	D15 ^a	D16-20 ^a	D22 ^a	D23-27 ^a	D29 ^a	D30-34 ^a	D36 ^a	D64 ^a	D104 ^a	
12-lead ECG	X		X	X		X		X		X		X		X	X	X	D1, D8, D15, D22, D29: pre-dose, then after end of study drug infusion D -1, D36, D104, E/D: time-matched with D1, D8, D15, D22, D29 pre-dose to the extent possible
AE monitoring				X	X	X	X	X	X	X	X	X	X	X	X	X	All AEs and SAEs will be collected from the time of the first study drug administration until D104.
Prior/concomitant medication review	X	X	X	X	X	X	X	X	X	X	X	X	X	X	X	X	
C-SSRS	X			X		X		X		X		X		X	X	X	
Clinical unit confinement		X	X	X		X		X		X		X					At least 6 hours following study drug administration on dosing days; discharge from the clinical unit will be at the discretion of the investigator provided there are no safety concerns identified from review of the clinical data. Optional overnight confinement from either D -2 or D -1 and on days prior to other dosing days (D7, D14, D21, D28)
Outpatient visit			X										X	X	X	X	If the patient is not overnight confined on D -1 (see above), the D -1 visit will be an outpatient visit

Table 6. Part 2 - Schedule of Activities

	Study Drug Administration Period													Notes			
	Screening D-28 to D-2 ^a	D-2 ^a	D-1 ^a	D1 ^a	D2-6 ^a	D8	D9-13 ^a	D15 ^a	D16-20 ^a	D22 ^a	D23-27 ^a	D29 ^a	D30-34 ^a	D36 ^a	D64 ^a	D104 ^a	E/D ^b
Site to contact patient					X	X	X	X	X	X	X	X					Investigator or designee to telephone the patient between D2-6, D9-13, D16-20, D23-27, and D30-34
Central Laboratory Assessments																	
Viral serology (HBsAg, IGM anti-HBc, anti-HCV, HIV) and COVID-19	X																
Urine alcohol	X		X							X	X						Locally performed at site
Drug screening	X		X							X	X						
Clinical laboratory tests (clinical chemistry, hematology, urinalysis)	X		X		X			X				X		X	X		
Pharmacodynamic Assessments: Cognition Testing, MRI, Blood Samples																	
MMSE	X		X				X					X	X	X	X		
Clinical Dementia Rating scale			X				X					X	X	X	X		
Cognitive Drug Research System battery ^d	X		X		X		X	X	X	X	X	X	X	X	X		
NPI			X									X	X	X	X		
Blood sample for PD assessment			X									X	X	X	X		Fluid biomarkers will be determined in plasma
Study Treatment																	
Study drug IV infusion				X	X	X	X	X	X								

Table 6. Part 2 - Schedule of Activities

	Screening	Study Drug Administration Period														Notes	
	D-28 to D-2 ^a	D-2 ^a	D-1 ^a	D1 ^a	D2-6 ^a	D8	D9-13 ^a	D15 ^a	D16-20 ^a	D22 ^a	D23-27 ^a	D29 ^a	D30-34 ^a	D36 ^a	D64 ^a	D104 ^a	
Pharmacokinetics																	
Blood sample for PK assessment				X							X		X	X	X	X	Pre-dose and the end of infusion on D1 and D29; single sample on other days
Blood sample for ADA assessment				X								X		X	X		ADA assessment is performed on blood sample collected for PK assessments; D1 assessment is performed on the pre-dose sample
Blood sample for ApoE4 genotyping	X																Optional ApoE4 sampling is collected at screening but can be taken at any visit until the last study visit (Section 8.7 of Protocol)

AD = Alzheimer's Disease; ADA = anti-drug antibody; AE = adverse event; anti-HCV = hepatitis C virus antibody; ApoE4 = apolipoprotein E4; COVID = coronavirus disease; CRF = case report form; C-SSRS = Columbia Suicide Severity Rating Scale; D = Day; DSM-5 = Diagnostic and Statistical Manual of Mental Disorders, Fifth Edition; ECG = electrocardiogram; E/D = Early Discontinuation; HBsAg = hepatitis B surface antigen; IgM anti-HBc = immunoglobulin M antibody to hepatitis B core antibody; IV = intravenous(Iy); MMSE = Mini-Mental State Examination; NINCDS-ADRDA = National Institute of Neurological and Communicative Disorders and Stroke – Alzheimer's Disease and Related Disorders Association; NPI = Neuropsychiatric Inventory; PD = pharmacodynamic(s); PK = pharmacokinetic(s); SAE = serious adverse event.

a Visit days and procedures are allowed a window of ± 2 days from Day 1 to End of Treatment.

b Applicable only for patients who discontinue early from the study.

c The medical history assessed at the screening visit should include prior AD treatment assessment(s). Establishing the clinical diagnosis of AD should include use of criteria from the DSM-5 – Criteria for Major Neurocognitive Disorder (previously dementia) (Section 10.3 of Protocol, Appendix 4) and the NINCDS-ADRDA (Note: ADRDA is now the Alzheimer's Association) (Section 10.4 of Protocol, Appendix 5).

d The Cognitive Drug Research battery is to be performed twice during the screening visit in both Part 1 and Part 2.

